8.1.6. Asthma Exacerbations

All asthma exacerbation data will be listed. Number of asthma exacerbations that occur while on-treatment (week 0-week 12) and number of asthma exacerbations that occur on-treatment and post-treatment (week 0 – week 20) will be summarised by mepolizumab dose group and mepolizumab overall. Additionally the number of asthma exacerbations that occur during Part B (Week 20 –Week 72) will be summarised by mepolizumab dose group and mepolizumab overall. Further summaries will be presented as listed in [Table 7](#).

8.1.7. Total Immunoglobulin-E (IgE)

Total IgE will be summarised by mepolizumab dose group and mepolizumab overall for each visit.

8.1.8. Total Interleukin-5 (IL-5)

Total IL-5 will be summarised by mepolizumab dose group and mepolizumab overall for each visit.

8.2. Safety Analyses

8.2.1. Overview of Planned Adverse Event Analyses

Safety analyses will be based on the Safety population unless otherwise specified in [Appendix 10: List of Data Displays](#). The safety displays to be created as part of the RAP include all the required and relevant displays identified as per the RAP Core Safety Reporting Template Version 1.0.

[Table 8](#) provides an overview of the planned analyses, with further details of data displays being presented in [Appendix 10: List of Data Displays](#). The same displays will be produced for both study Part A and study Part B data.

Adverse events will be coded using the latest version of the Medical Dictionary for Regulatory Activities (MedDRA).

Table 8 Overview of Planned Adverse Event Analyses

Endpoint	Absolute			
	Summary		Individual	
	T	F	F	L
Exposure				
Number of treatments administered and time on-treatment	Y			Y
Adverse Event				
Overview of Adverse Events	Y			
AEs by SOC and Maximum Intensity	Y			Y
On-Treatment AEs by Overall Frequency	Y			
All Drug-Related AEs by SOC and Maximum Intensity	Y			
Number of subjects & occurrences of common non-serious AEs ^[1] by SOC and PT	Y			
Subject Numbers for Individual AEs				Y
Relationship between AE SOCs, PT & verbatim text				Y
AEs by Highest Antidrug Antibody Result At Any Time Post Baseline	Y			
Serious and Other Significant AEs				
Fatal Serious AEs	Y			Y
Non-Fatal Serious AEs	Y			Y
Reasons for Considering as a Serious Adverse Event				Y
Serious AEs by SOC	Y			
Drug-Related Serious AEs by SOC and Maximum Intensity	Y			
AEs leading to Permanent Discontinuation of Study Treatment or Withdrawal from Study by Overall Frequency	Y			Y
Number of Subjects and Occurrences of Serious, Drug-Related Serious, Fatal Serious, and Drug-Related Fatal Serious AEs	Y			
AEs of Special Interest (On-Treatment) ^[2]				
Systemic Reactions (Hypersensitivity and Non-Allergic)	Y			Y
Local Injection Site Reactions	Y			Y
AEs meeting Anaphylaxis Criteria	Y			Y
Serious Cardiac, Vascular and Thromboembolic (CVT) AEs	Y			Y
Serious Ischemic AEs	Y			Y
Malignancies	Y			Y
Opportunistic Infections	Y			Y
Cardiovascular Events				
All Cardiovascular Events	Y			Y

NOTES :

- T = Table, F = Figure, L = Listing, Y = Yes display generated. PT = Preferred Term, SOC = System Organ Class
- Summary = Represents TFL related to any summaries (i.e. descriptive statistics) of the observed raw data.
- Individual = Represents FL related to any displays of individual subject observed raw data.

^[1] Common AEs will be defined as AEs with frequency $\geq 3\%$ (prior to rounding to nearest percent) in overall mepolizumab treatment group.

^[2] On-treatment Summary Profiles of each type of AE of Special Interest will also be presented.

8.2.1.1. Adverse Events of Special Interest

Adverse events of special interest (AESIs) are adverse events associated with the identified and potential risks of mepolizumab. AESIs of anaphylaxis reactions, systemic reactions, and local injection site reactions are collected via targeted eCRF within the

study. Events captured on the eCRF as systemic reactions will be further categorized as allergic/hypersensitivity reactions or non-allergic reactions. Events with preferred terms such as injection related reaction or administration related reaction will be considered non-allergic reactions. All remaining events will be considered allergic/hypersensitivity reactions.

AESIs of opportunistic infections, malignancies, serious CVT events and serious ischemic events will be identified from a list of relevant preferred terms maintained within a project level reference dataset created based on the MedDRA dictionary available at the time of database freeze for this study, further details of how relevant preferred terms are identified are given in the Program Safety Analysis Plan (PSAP).

Separate summary tables showing the number and percent of subjects with each type of AESI, broken down by preferred term will be created. Information will be reported as part of the standard AE tables for AESIs of infections, serious infections, neoplasms, cardiac disorders and serious cardiac disorders.

For each type of AESI a profile summary table will be produced containing information which would include, but not be limited to, the number of occurrences of the event, event characteristics, time to onset, intensity, outcome and action taken.

A listing of any subjects with systemic events identified by the investigators as meeting the criteria for anaphylaxis as outlined by the 2006 Joint National Institute of Allergy and Infectious Disease/Food Allergy and Anaphylaxis Network Second Symposium on Anaphylaxis [[Sampson, 2006](#)] will be provided.

8.2.1.2. Cardiovascular Events

Cardiovascular events will be captured on targeted CV event pages of the CRF for the following AEs and SAEs:

- Myocardial infarction/unstable angina
- Congestive heart failure
- Arrhythmias
- Valvulopathy
- Pulmonary hypertension
- Cerebrovascular events/stroke and transient ischemic attack
- Peripheral arterial thromboembolism
- Deep venous thrombosis/pulmonary embolism
- Revascularization

8.2.2. Overview of Planned Clinical Laboratory Analyses

Safety analyses will be based on the Safety population unless otherwise specified in [Appendix 10](#): List of Data Displays. The safety displays to be created as part of the RAP include all the required and relevant displays identified as per the RAP Core Safety Reporting Template Version 1.0.

Table 9 provides an overview of the planned analyses, with further details of data displays being presented in Appendix 10: List of Data Displays.

Table 9 Overview of Planned Clinical Laboratory Analyses

Endpoint	Absolute				Change from Baseline			
	Summary		Individual		Summary		Individual	
	T	F	F	L	T	F	F	L
Immunogenicity								
Immunogenicity (ADA and NAb results)	Y			Y				
Treatment Emergent ADA results	Y							
Clinical Chemistry								
Change from Baseline in Clinical Chemistry by Visit					Y			
Chemistry Results (Change from Baseline Relative to Normal Range)	Y				Y			
Haematology								
Change from Baseline in Haematology by Visit					Y			
Haematology Results (Change from Baseline Relative to Normal Range)	Y				Y			
Urinalysis								
Urinalysis Data				Y				
Hepatobiliary (Liver)								
Liver Monitoring/Stopping Event Reporting				Y				
Chemistry Results for Subjects Meeting Liver Monitoring/Stopping Event Criteria				Y				
Medical Conditions for Subjects with Liver Stopping Events				Y				
Listing of Substance Use for Subjects with Liver Stopping Events				Y				
Hepatobiliary Laboratory Abnormalities	Y			Y				
Scatter Plot of Maximum vs. Baseline for ALT		Y						
Scatter Plot of Maximum ALT vs. Maximum Total Bilirubin		Y						

NOTES :

- T = Table, F = Figure, L = Listing, Y = Yes display generated.
- Summary = Represents TF related to any summaries (i.e. descriptive statistics) of the observed raw data.
- Individual = Represents FL related to any displays of individual subject observed raw data.

8.2.2.1. Immunogenicity

Immunogenicity is a measure of the immune response to a therapeutic drug (e.g. a monoclonal antibody) resulting in generation of anti-drug antibodies. Clinical samples are tested in a sequence of binding anti-drug antibody (ADA) and neutralising antibody assays:

- a) Screening assay. Each sample is tested for the presence of anti-drug antibodies (ADA assay) and initially declared positive or negative according to assay cut-off criteria. Negative samples are not tested further. Positive samples are then tested in the confirmation ADA assay.
- b) Confirmation assay. Each positive sample from the screening assay is either confirmed positive in this assay (ADA assay), or is declared negative and are not tested further. Positive ADA samples are then tested in the titer assay and neutralization (NAb) assay.
- c) Titration assay. Each positive sample from the ADA confirmation assay is serially diluted to provide a titre, corresponding to the highest dilution factor that still yields a positive test result.
- d) Neutralising assay. Each positive sample from the ADA confirmation assay is tested with the neutralising antibody assay and found as either positive or negative in this assay (NAb assay).

The mepolizumab ADA (screening/confirmation/titration) assay version 2011N122789 is performed at a Alliance Pharma (method 120711M01.V02). The mepolizumab Nab assay version 2011n129752 is being performed within GSK.

- A table will be produced summarising the number and percentage of negative and confirmed positive subjects ADA samples by treatment group and visit in the Safety population. The table will also summarise the highest assay result obtained post-baseline for each subject.
- A similar table will also be produced summarising results for the neutralising antibody assay in the Safety Population, by treatment group and visit.
- An additional summary of treatment emergent positive confirmatory binding antibody assay and results in the subset of subjects who did not have a positive confirmatory binding antibody assay result prior to the first dose of study treatment will also be presented.
- All immunogenicity results (i.e. ADA screening and confirmatory assay results, titre values, neutralising antibody results and observed mepolizumab concentration) will be listed.

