
 To assess the long-term (52 weeks) safety and tolerability of mepolizumab when administered subcutaneously to subjects aged 6 to 11* years old with severe eosinophilic asthma 	
 Incidence of Adverse Events Frequency of positive anti-mepolizumab binding antibodies and neutralizing antibodies Incidence of clinically significant changes in vital sign measurements Incidence of clinically significant changes in clinical laboratory parameters
Secondary	

 To characterize the long-term (52 weeks) durability of pharmacodynamics of mepolizumab administered subcutaneously to subjects aged 6 to 11* years old with severe eosinophilic asthma 	
 Change from Week 0 (Visit 2) in absolute blood eosinophil count at weeks 32, 44, 56, 68, 72 and 80**.
Exploratory	

 To assess the number of asthma exacerbations that occur during the long-term (52 weeks) part of the study following subcutaneous administration of mepolizumab to subjects aged 6 to 11* years old with severe eosinophilic asthma To characterize the long-term (52 weeks) asthma control following subcutaneous administration of mepolizumab to subjects aged 6 to 11* years old with severe eosinophilic asthma 	
 Incidence of asthma exacerbations Change from Week 0 (Visit 2) in ACQ-7 and C-ACT at weeks 32, 44, 56, 68, 72 and 80**.

*Subjects who reach their 12th birthday during Part A may participate in Part B

**Week 80 is not applicable to subjects transitioning to the long-term access program

Overall Design

Pharmacokinetic/Pharmacodynamic Phase (Part A)

This is a multi-centre, open-label study that will assess the pharmacokinetics and pharmacodynamics of three 4-weekly doses of mepolizumab, either 40 or 100mg depending on subject bodyweight, administered SC to subjects with severe eosinophilic asthma aged 6-11 years.

Long-Term Safety / Pharmacodynamic Phase (Part B)

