3.90.	Safety	AE3	Summary of Opportunistic Infections (On-Treatment) (Part B)	Footnote 'Events matching terms based on a published list considered as opportunistic infections in the setting of biologic therapy [Winthrop, 2015]'	SAC

Safety Tables					
No.	Population	IDSL / TST ID / Example Shell	Title	Programming Notes	Deliverable [Priority]
3.91.	Safety		Summary Profile of Opportunistic Infections (On-Treatment) (Part B)	See format of Safety Table 3.39 (200862 'final' reporting effort) Footnote 'Events matching terms based on a published list considered as opportunistic infections in the setting of biologic therapy [Winthrop, 2015]'	SAC
3.92.	Safety		Summary of Serious AEs and AEs of Special Interest (Part B)	See format of Safety Table 3.40 (200862 'final' reporting effort) Do not include Relative Risk or % Risk Difference columns	SAC
Cardiovascular Events					
3.93.	Safety		Summary of All Cardiovascular Events Reported by the Investigator (Part B)	See format of Safety Table 3.11 (200862 'final' reporting effort)	SAC
Immunogenicity					
3.94.	Safety		Summary of ADA Assay Results (Part B)	See format of Safety Table 3.41 (200862 'final' reporting effort)	SAC
3.95.	Safety		Summary of NAb Assay Results (Part B)	See format of Safety Table 3.42 (200862 'final' reporting effort)	SAC
3.96.	Safety		Summary of Treatment Emergent ADA Assay Results (Part B)	See format of Safety Table 3.41 (200862 'final' reporting effort)	SAC
Laboratory Data					
3.97.	Safety	LB1	Summary of Change From Baseline in Chemistry Data (Part B)	Include Baseline values	SAC
3.98.	Safety	LB3	Summary of Chemistry Results (Change from Baseline Relative to the Normal Range) (Part B)		SAC
3.99.	Safety	LB1	Summary of Change From Baseline in Haematology Data (Part B)	Include Baseline values	SAC

Safety Tables					
No.	Population	IDSL / TST ID / Example Shell	Title	Programming Notes	Deliverable [Priority]
3.100.	Safety	LB3	Summary of Haematology Results (Change from Baseline Relative to the Normal Range) (Part B)		SAC
Hepatobiliary (Liver)					
3.101.	Safety	LIVER10	Summary of Subjects Meeting Emergent Hepatobiliary Laboratory Abnormality Criteria (Part A)		SAC
Electrocardiogram (ECG)					
3.102.	Safety	EG1	Summary of ECG Findings (Part B)		SAC
3.103.	Safety	EG2	Summary of Change from Baseline ECG Values by Visit (Part B)	Include Baseline values	SAC

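### The treatment-emergent antibody table leaves out children already positive before dosing, and no specified summary compares titre with baseline, so a boosted response can be recognised only from the listings.

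*SAP*

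**What the plan says.** SAP section 8.2.2.1 plans three summaries and a listing.

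- An ADA table "summarising the number and percentage of negative and confirmed positive subjects ADA samples by treatment group and visit in the Safety population". The text adds: "The table will also summarise the highest assay result obtained post-baseline for each subject". These are Tables 3.41 and 3.94.
- A neutralising antibody (NAb) table: "A similar table will also be produced summarising results for the neutralising antibody assay in the Safety Population, by treatment group and visit". These are Tables 3.42 and 3.95.
- An additional treatment-emergent table, restricted to results "in the subset of subjects who did not have a positive confirmatory binding antibody assay result prior to the first dose of study treatment". These are Tables 3.43 and 3.96.
- A listing: "All immunogenicity results (i.e. ADA screening and confirmatory assay results, titre values, neutralising antibody results and observed mepolizumab concentration) will be listed". These are Listings 36 and 82.

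On titration, the same section says: "Each positive sample from the ADA confirmation assay is serially diluted to provide a titre". Titre values are then named only in the listing. SAP Table 9 plans immunogenicity as absolute tables and a listing, with no change-from-baseline display. Neither document defines a boosted response or a titre rise that would count as one.

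The endpoint served is "Frequency of positive anti-mepolizumab binding antibodies and neutralizing antibodies", which is primary in Part B and secondary in Part A.

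**The concern.** The study has no control arm. Separating antibody caused by the drug from antibody that was already there depends on comparing each child with his or her own pre-dose result. The treatment-emergent table is the display meant to do that, yet it removes baseline-positive children from both numerator and denominator. One way the drug can act on antibody, by raising the titre of an existing response, is therefore excluded by definition.

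Baseline positives are plausible. No eligibility criterion excludes pre-existing ADA. Exclusion criteria 11, 12 and 15 bar earlier biologics or investigational products only within a washout, and footnote 4 of protocol Table 3 expects some histories to include investigational anti-IL5 or anti-IL13 products. The sponsor also treats titre as informative: the immunogenicity row of protocol Table 1 cites titre as well as incidence from completed studies.

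At stake is whether the report can say how many children had an antibody response attributable to treatment.

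**Working it through.** The plan states no figure on this point, so there is none to reproduce. The check follows one child through the planned displays and then gives a sense of scale.

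**Where a baseline-positive, boosted child appears**

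| Display | Child included? | Boost visible? |
|---|---|---|
| ADA by visit (3.41, 3.94) | Yes, as positive | No: positive before and after |
| Highest post-baseline result (same tables) | Yes | Not specified: the term is undefined and no comparison with baseline is stated |
| NAb (3.42, 3.95) | Positive if neutralising | No titre comparison specified |
| Adverse events by highest post-baseline ADA result (3.10, 3.11, 3.63, 3.64) | Yes | No comparison with baseline specified |
| Treatment-emergent ADA (3.43, 3.96) | No | No |
| Listings 36 and 82 | Yes, with titres | Yes, by reading each child's record |

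The comparison is feasible. Protocol section 7.5 provides a pre-dose sample at Week 0 and later samples at Weeks 16 and 20 in Part A and Weeks 44, 68 and, where applicable, 80 in Part B. Every confirmed positive sample is titrated. SAP section 10.5.2.1 uses the same pre-treatment baseline for both parts.

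**Inputs for scale.** About 28 children treated (protocol section 4.3). Baseline ADA prevalence p is not given, so 1% to 10% is assumed.

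Chance that at least one of 28 is baseline-positive = 1 − (1 − p)^28:

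- p = 1%: 24.5%
- p = 2%: 43.2%
- p = 5%: 76.2%
- p = 10%: 94.8%

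**Effect on the reported figure** (28 children, boosting assumed as shown):

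| Boosted | Newly positive | As planned | Induced plus boosted |
|---|---|---|---|
| 1 | 0 | 0/27 = 0% | 1/28 = 3.6% |
| 1 | 1 | 1/27 = 3.7% | 2/28 = 7.1% |
| 2 | 1 | 1/26 = 3.8% | 3/28 = 10.7% |

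Exact 95% limits for the first row:

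- 0/27: upper limit 1 − 0.025^(1/27) = 12.8%, so 0 to 12.8%.
- 1/28: lower limit 1 − 0.975^(1/28) = 0.1%. The upper limit solves (1 − p)^28 + 28p(1 − p)^27 = 0.025, giving 18.3%.

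**The percentage can also move the other way**

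- If one child is baseline-positive but not boosted and three are newly positive, the plan gives 3/27 = 11.1%, against 3/28 = 10.7% with the wider denominator.
- The subset is defined by not having a positive pre-dose result, which a child with no pre-dose sample also satisfies. An antibody that child already carried would be counted as treatment-emergent.

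**The case against.** The strongest reply is that the endpoint is the frequency of positive antibodies, which Tables 3.41/3.42 and 3.94/3.95 deliver for the whole Safety population without excluding anyone. The treatment-emergent table is an additional summary, no endpoint mentions titre or boosting, and no hypothesis is tested. With about 28 children, a titre rise in one or two can be read directly from the listings. All of this stands, and it is why the point is small.

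It is also fair that the table layouts are borrowed from another study and the mock shells sit in supplementary material outside the two documents. The highest-result row might show titre. Even so, the SAP does not say that it would be set against the child's own baseline.

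Two stronger readings are tempting, and neither is supported. A reader might infer that a boosted child is counted in no summary. In fact the child is counted as positive in the all-subject ADA table, in the NAb table if neutralising, and in the adverse-event tables by ADA result. A reader might also infer that the treatment-emergent figure can only err low. The percentage can run slightly high when an unboosted baseline-positive child leaves the denominator, or when a child without a baseline sample is admitted.

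What the reply does not answer is that the one table meant to isolate drug-related antibody excludes one form of it by rule, although the data to include it are already generated.

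**Conclusion.** The concern holds as a minor gap in definition. Tables 3.43 and 3.96 exclude every child confirmed positive before dosing, and no specified summary uses titre change. A boosted response therefore cannot be separated from an unchanged pre-existing one except by reading the listings. The frequency endpoint is not lost.

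One child is 3.6 percentage points of 28. The illustrated shift from 0/27 to 1/28 rests on assuming exactly one baseline-positive, boosted child and no new positives, and the two intervals overlap heavily. The documents give no baseline prevalence. If it is zero, the two definitions give the same count. The protocol sets no sample size for Part B, so the figure of 28 applies to Part A only and the weight of one child in Part B is unknown.

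**What to change.** In SAP section 8.2.2.1, define treatment-emergent ADA as either:

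- **treatment-induced:** confirmed negative at baseline and confirmed positive at any later visit; or
- **treatment-boosted:** confirmed positive at baseline, with a post-baseline titre above a stated multiple of the baseline titre.

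Take the multiple from the assay's own dilution steps and fix it before database freeze. Neither document gives those steps, so no value is proposed here. In Tables 3.43 and 3.96, report induced, boosted and total as separate rows. Use as denominator all children with both a baseline and a post-baseline result, which also settles how a missing baseline is handled.

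No new samples or assays are needed. The cost is a short addition to the SAP text, extra rows in two tables, a threshold to be obtained from the assay documentation, and a small departure from the borrowed table layout.

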8.2.3. Overview of Planned Other Safety Analyses

The safety analyses will be based on the Safety population unless otherwise specified in [Appendix 10: List of Data Displays](#). The safety displays to be created as part of the RAP include all the required and relevant displays identified as per the RAP Core Safety Reporting Template Version 1.0.

[Table 10](#) provides an overview of the planned analyses, with further details of data displays being presented in [Appendix 10: List of Data Displays](#).

Table 10 Overview of Planned Other Safety Analyses

Endpoint	Absolute				Change from Baseline			
	Summary		Individual		Summary		Individual	
	T	F	F	L	T	F	F	L
ECG								
ECG Findings	Y			Y				
Change from Baseline in ECG Values by Visit					Y			
Actual and Change From Baseline QTc(F) Values by Category	Y				Y			
Vital Signs								
Change From Baseline in Vital Signs by Visit					Y			

NOTES :

- T = Table, F = Figure, L = Listing, Y = Yes display generated.
- Summary = Represents TF related to any summaries (i.e. descriptive statistics) of the observed raw data.
- Individual = Represents FL related to any displays of individual subject observed raw data.

